conducted in 1,326 IVF/ICSI patients who were randomised 1:1 to controlled ovarian stimulation with one of the following treatments: 1) FE 999049 in its individualised dosing regimen with the daily dose fixed throughout stimulation, or 2) an approved CHO-derived rFSH product (follitropin alfa, GONAL-F) at a standard starting dose of 150 IU/day followed by dose adjustments based on the subject's follicular response during stimulation. FE 999049 in its individualised dosing regimen was demonstrated to be non-inferior to follitropin alfa with respect to ongoing pregnancy rate (30.7% versus 31.6%) and ongoing implantation rate (35.2% versus 35.8%). For the overall population, there was no statistically significant difference between treatment groups in terms of number of oocytes retrieved, with an average of 10.0 for FE 999049 and 10.4 for follitropin alfa. Nevertheless, the individualised FE 999049 dosing regimen in comparison to follitropin alfa led to statistically significantly more oocytes retrieved among patients with AMH <15 pmol/L (population at risk of hyporesponse) with an average of 8.0 versus 7.0 and statistically significantly fewer oocytes among patients with AMH ≥15 pmol/L (population at risk of hyperresponse) with an average of 11.6 versus 13.3. The immediate clinical relevance of this shift in ovarian response with FE 999049 therapy was realised as statistically significantly fewer patients with extreme ovarian response compared to follitropin alfa, i.e. <4 oocytes among patients with AMH <15 pmol/L (12% versus 18%) and ≥15 or ≥20 oocytes among patients with AMH ≥15 pmol/L (28% versus 35%, and 10% versus 16%). The percentage of patients with an appropriate ovarian response, defined for FE 999049 as 8-14 oocytes, was reached by statistically significantly more patients treated with FE 999049 compared to follitropin alfa, i.e. 43% versus 38%, despite implementation of dose adjustments during stimulation for 37% of the patients in the follitropin alfa group in contrast to the fixed-dose individualised dosing regimen for FE 999049. A statistically significantly lower total gonadotropin dose in the FE 999049 group compared to the CHO-derived rFSH product group was observed with an average of 90 µg and 104 µg, respectively.

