The most serious risk associated with gonadotropin treatment is ovarian hyperstimulation syndrome (OHSS). Overall in the phase 3 trials overseas, OHSS and/or preventive interventions of early OHSS occurred in 4.4% of the FE 999049 cycles and 6.5% of the follitropin alfa cycles. Moderate/severe OHSS and/or preventive interventions for early OHSS were observed at an incidence of 3.3% and 5.6% of the treatment cycles with FE 999049 and follitropin alfa, respectively.

Previous studies have reported OHSS rates in Japanese patients between 5% and 28.3%.^{5,6,7} In the FE 999049 phase 2 trial in Japan, the incidence of early moderate/severe OHSS was 19.5% for subjects in the FOLLISTIM group. Despite the variation in the OHSS incidence reporting, the high OHSS incidence in Japanese IVF/ICSI patients illustrates a clear need in Japan for a treatment option with a safer OHSS profile. Based on more than 1,300 cycles in the ESTHER-1 phase 3 trial, the individualised dosing regimen of FE 999049 was associated with a statistically significant reduction in the proportion of subjects with early OHSS and/or preventive interventions for early OHSS in comparison to the standard regimen of CHO-derived rFSH product, with an incidence of 4.7% in the FE 999049 group and 6.2% in the follitropin alfa group. For further information regarding FE 999049, please refer to the Investigator's Brochure.⁸

The present trial aims to establish non-inferiority of FE 999049 versus FOLLISTIM with respect to number of oocytes retrieved and will document the efficacy and safety of FE 999049 in Japanese IVF/ICSI patients.

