9.7.4 Secondary Endpoints

Secondary endpoints will be evaluated based on the FAS.

Positive β hCG Rate

Positive β hCG is defined as positive serum β hCG test 13-15 days after transfer. The positive β hCG rate will be summarised and analysed in a similar manner as the clinical pregnancy rate.

Vital Pregnancy Rate

Vital pregnancy is defined as at least one intrauterine gestational sac with fetal heart beat 5-6 weeks after transfer. The vital pregnancy rate will be summarised and analysed in a similar manner as the clinical pregnancy rate. For subjects with a vital pregnancy, the number of intrauterine gestational sacs with fetal heart beat and the number of fetuses with fetal heart beat will be tabulated.

Implantation Rate

Implantation rate is defined as the number of gestational sacs 5-6 weeks after transfer divided by number of blastocysts transferred. The implantation rate will be summarised and analysed in a similar manner as the vital pregnancy rate. The transferred blastocysts are the experimental unit.

Cycle Cancellation due to Poor or Excessive Ovarian Response or Blastocyst Transfer Cancellation due to Excessive Ovarian Response / OHSS Risk

For this endpoint, treatment groups will be compared using a logistic regression model with treatment and AMH stratum as fixed factors. If both factors are significant then the possibility of an interaction will be investigated. The difference between treatments will be reported as an odds ratio including 95% confidence interval and p-value for test of no treatment difference. If the expected number of observations is less than five in any of the cells in the contingency table then Fisher's exact test will be used as alternative.

The analysis will be performed for the composite endpoint and the separate components defined as: the proportion of subjects with cycle cancellation due to poor ovarian response, the proportion of subjects with cycle cancellation due to excessive ovarian response, the proportion of subjects with cycle cancellation due to poor or excessive ovarian response, the proportion of subjects with blastocyst transfer cancellation due to excessive ovarian response/ OHSS risk.

Ovarian Response

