9.2.2 Sensitivity Analyses and Additional Analysis

The FAS is the primary analysis population for this trial, and the analysis of the PP analysis set is only considered supportive for the application in Japan. In the EMA guideline “Points to consider on switching between superiority and non-inferiority”¹, the FAS and the PP analysis sets are considered equally important. FE 999049 is a compound under global development. Therefore, for applications in countries applying the EMA guideline, Ferring would intend to demonstrate non-inferiority for both the FAS and PP analysis sets, and in such a case both would be considered as confirmatory analyses.

The primary analysis will therefore be repeated using the PP analysis set. This sensitivity analysis will address the assay sensitivity of the primary analysis by excluding subjects with major protocol deviations, e.g. substantial non-compliance with randomised treatment.

To investigate the possibility for different treatment differences in the two AMH strata, an analysis of variance model will be fitted where the treatment-by-stratum interaction is included. In addition, subgroup analyses will be performed for the two AMH strata separately (using a simpler model with only treatment as factor). The trial is not powered to show non-inferiority in the two strata separately and these analyses should only be regarded as descriptive.

Additional descriptions will be made based only on subjects with oocytes retrieved. The purpose of this is purely descriptive.

The percentage of subjects with <4 oocytes, 4-7 oocytes, 8-14 oocytes, 15-19 oocytes, and >20 oocytes retrieved will be tabulated both for all subjects in the FAS and for the two AMH strata.

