9.4 Secondary Endpoints

Secondary efficacy endpoints will be evaluated based on the FAS only.

Statistical tests will be performed using a two-sided test at a 5% significance level. Treatment differences will (where appropriate) be presented with 95% confidence intervals and p-values

corresponding to the statistical test of the hypothesis of 'equal effect' against the alternative of 'different effect'.

Positive β hCG Rate

Positive β hCG is defined as positive serum β hCG test 13-15 days after transfer. The positive β hCG rate will be summarised and analysed in a similar manner as the clinical pregnancy rate.

Vital Pregnancy Rate

Vital pregnancy is defined as at least one intrauterine gestational sac with fetal heart beat 5-6 weeks after transfer. The vital pregnancy rate will be summarised and analysed in a similar manner as the clinical pregnancy rate. For subjects with a vital pregnancy, the number of intrauterine gestational sacs with fetal heart beat and the number of fetuses with fetal heart beat will be tabulated.

Implantation Rate

Implantation rate is defined as the number of gestational sacs 5-6 weeks after transfer divided by number of blastocysts transferred. The implantation rate will be summarised and analysed in a similar manner as the vital pregnancy rate. The transferred blastocysts are the experimental unit. Note that since single blastocyst transfer is mandatory in this trial, these descriptions and analyses are likely to be identical to a description and analysis of the clinical pregnancy rate in the subgroup of subjects that had a blastocyst transfer.

Cycle Cancellation due to Poor or Excessive Ovarian Response or Blastocyst Transfer Cancellation due to Excessive Ovarian Response / OHSS Risk

For this endpoint, treatment groups will be compared using a logistic regression model with treatment and AMH stratum as fixed factors. The difference between treatments will be reported as an odds ratio including 95% confidence interval and p-value for test of no treatment difference. In case of sparse data, treatments will be compared using the Cochran-Mantel-Haenszel test stratified for AMH stratum. Within AMH stratum the comparisons will be based on Fisher's exact test.

If both the factors treatment and AMH stratum are significant in the logistic regression analysis the possibility of a treatment-by-AMH interaction will be investigated.

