The analysis will be performed for the composite endpoint (all cancellations of either the cycle due to poor or excessive response, or of the transfer due to excessive ovarian response/OHSS risk) and each of the separate components defined as: the proportion of subjects with cycle cancellation due to poor ovarian response, the proportion of subjects with cycle cancellation due to excessive ovarian response, the proportion of subjects with cycle cancellation due to poor or excessive ovarian response, the proportion of subjects with blastocyst transfer cancellation due to excessive ovarian response/OHSS risk, and the combination of cycle cancellations due to excessive response and transfer cancellation due to excessive ovarian response/OHSS risk.

Ovarian Response

The number of oocytes retrieved will be tabulated with subjects grouped according to number of oocytes retrieved (<4 (low response), 4-7 (moderate response), 8-14 (targeted response), 15-19 (hyperresponse) and ≥ 20 (severe hyperresponse)). Subjects with cycle cancellation due to poor ovarian response will be included in the <4 oocytes group. Subjects with cycle cancellation due to excessive ovarian response will here be included in the ≥ 20 oocytes group. For each definition the proportion of subjects will be tabulated. These endpoints will be analysed in a similar manner as the proportion of subjects with cycle cancellation.

Extreme Ovarian Response

The analyses of extreme ovarian response will be performed using the following definitions of extreme ovarian response: <4 oocytes retrieved, ≥ 15 oocytes retrieved, ≥ 20 oocytes retrieved, <4 or ≥ 15 oocytes retrieved and <4 or ≥ 20 oocytes retrieved. Subjects with cycle cancellation due to poor ovarian response will be included as <4 oocytes retrieved. Subjects with cycle cancellation due to excessive ovarian response will be included as ≥ 15 and ≥ 20 oocytes retrieved.

For each definition the proportion of subjects with extreme ovarian response will be tabulated. These endpoints will be analysed in a similar manner as the proportion of subjects with cycle cancellation. In addition, they will be analysed based on all subjects with triggering of final follicular maturation.

Number and Size of Follicles during Stimulation

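### For fewer than 4 and for 15 or more oocytes, report the treatment-by-AMH interaction whatever the main-effect p-values; the pooled treatment effect is a poor screen for it

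*SAP*

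**What the plan says.** SAP 9.4, under cycle cancellation, compares treatments by logistic regression with treatment and AMH stratum as fixed factors, and adds: "If both the factors treatment and AMH stratum are significant in the logistic regression analysis the possibility of a treatment-by-AMH interaction will be investigated". Protocol 9.7.4 has the same rule: "If both factors are significant then the possibility of an interaction will be investigated".

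Under both Ovarian Response and Extreme Ovarian Response, SAP 9.4 then states: "These endpoints will be analysed in a similar manner as the proportion of subjects with cycle cancellation". Extreme response includes fewer than 4 and 15 or more oocytes. The natural reading is that the conditional interaction step comes with the rest of the method, although the SAP does not spell this out.

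Other parts of the SAP carry no such condition. For the oocyte count, SAP 9.2.2 says "an analysis of variance model will be fitted where the treatment-by-stratum interaction is included". SAP 9.1 presents treatment comparisons for secondary efficacy endpoints by AMH stratum in every case.

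**The concern.** Whether treatment has an effect on average and whether its effect differs between strata are separate questions. If FE 999049 lowers a risk in one stratum and raises it in the other, the two partly cancel in the main-effects model. The condition is then least likely to be met when the interaction is of most interest.

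The documents give reason to expect something of this kind. Protocol 1.1 reports that in the overseas phase 3 trial (ESTHER-1) "there was no statistically significant difference between treatment groups in terms of number of oocytes retrieved" (10.0 versus 10.4). Yet FE 999049 gave more oocytes below 15 pmol/L, "with an average of 8.0 versus 7.0 and statistically significantly fewer oocytes among patients with AMH" of 15 pmol/L or more (11.6 versus 13.3).

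What is at stake is the formal estimate and test of interaction for two dichotomised secondary endpoints. Separate p-values in each stratum do not show whether the effects differ.

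**Working it through.** **The plan's own figure.** SAP 3.2: margin 3.0, SD 8.1, true difference 0, one-sided 2.5%, 90% power. n = 2 × (1.960 + 1.282)² × 8.1² / 3.0² = 153.2, so 154 per arm by the normal approximation and 155 by the t-test (power 90.2%). 155 / 0.95 = 163.2, so 164 per arm and 328 in total. This reproduces. The plan gives no power for any interaction.

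**Inputs from the documents.** 164 per arm; two-sided 5% tests (SAP 9.4). ESTHER-1 rates, FE 999049 versus comparator (protocol 1.1): fewer than 4 oocytes, AMH <15, 12% v 18%; 15 or more, AMH ≥15, 28% v 35%.

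**Assumed inputs.**
- Share of subjects with AMH <15: 30, 45 or 60%. The ESTHER-1 means imply (11.6 − 10.0)/(11.6 − 8.0) = 0.44 and (13.3 − 10.4)/(13.3 − 7.0) = 0.46.
- Rates in the stratum not reported, from negative binomial fits to the means: fewer than 4 in high AMH, 5.2% v 2.8%; 15 or more in low AMH, 7.1% v 4.3%.

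**Odds ratios.** Fewer than 4: (12/88)/(18/82) = 0.62 in low AMH and (5.2/94.8)/(2.8/97.2) = 1.90 in high. 15 or more: (28/72)/(35/65) = 0.72 in high AMH and (7.1/92.9)/(4.3/95.7) = 1.70 in low.

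**Cancellation at a 45% low-AMH share.** Fewer than 4: 0.45 × 12 + 0.55 × 5.2 = 8.3% v 0.45 × 18 + 0.55 × 2.8 = 9.6%. Differences of −6 and +2.4 points pool to about −1.4.

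**Simulation.** 20,000 trials per scenario, likelihood ratio tests at 5%. The condition is met when treatment and AMH stratum both have p<0.05 in the main-effects model. Entries are percentages of trials at low-AMH shares of 30/45/60%; lost = unconditional minus both.

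| Scenario | Condition met | Unconditional interaction p<0.05 | Both | Lost |
|---|---|---|---|---|
| <4: low 12 v 18, high 5.2 v 2.8 | 4.9/7.3/12.4 | 25.6/25.9/23.8 | 1.2/1.9/2.7 | 24.4/24.0/21.1 |
| ≥15: high 28 v 35, low 7.1 v 4.3 | 15.1/9.6/6.0 | 17.6/20.9/22.6 | 2.6/2.0/1.3 | 15.0/18.9/21.3 |

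AMH stratum is significant in about nine in ten of these trials or more, so the pooled treatment term is what blocks. For fewer than 4 oocytes with a common odds ratio and no interaction, the condition is met in 16-23% of trials, more often than under opposition.

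**Sensitivity.**

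| Scenario | Condition met | Unconditional interaction p<0.05 |
|---|---|---|
| <4: low 12 v 18, no effect in high (4 v 4) | 9.8/13.5/18.8 | 9.6/10.4/9.8 |
| ≥15: high 28 v 35, no effect in low (5 v 5) | 19.5/15.8/12.2 | 8.5/8.1/8.2 |
| ≥15: high 25 v 45, low 7.1 v 4.3 | 82.5/63.7/38.2 | 35.0/45.4/50.8 |
| ≥15: high 25 v 45, low 12 v 6 | 74.4/46.8/18.9 | 57.6/70.5/75.5 |

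With no effect in the other stratum, at most about 10 points can be lost. The larger high-AMH contrast is included because protocol 1.1 says that in the Japanese phase 2 trial "the incidence of early moderate/severe OHSS was 19.5% for subjects in the FOLLISTIM group". There the condition hides 17-82% of significant interactions. The absolute loss is not always smaller: in the last row at a 60% share it is at least 75.5 − 18.9 = 56.6 points.

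**Precision.** The 95% CI for the ratio of odds ratios multiplies and divides the estimate by exp(1.96 × SE), with SE² the sum of reciprocal cell counts (0.5 added to each). At the rates in the first table the median factor is 6.0/6.0/7.2 for fewer than 4 and 6.5/4.8/4.2 for 15 or more.

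**The case against.** - **The cross-reference may not carry the condition.** Where SAP 10.3 spells out the same phrase for OHSS, it names only the two-factor logistic model and no interaction step. On that reading these two endpoints have no interaction step at all. This stands as an uncertainty; the added sentence settles it either way.
- **The clinical question is largely covered.** For +1.0 versus −1.7 oocytes, the count interaction has z = 2.7/√(2 × SD² × (1/n_low + 1/n_high)). At SD 8.1 and 74/90 per arm, z = 2.7/1.80 = 1.50 and power is about 32% (28-32% over the three shares). With SDs of 4.5 and 6 it is 60-64%. This largely stands: the SAP already runs the stronger test. The count is not a full substitute, because SAP 9.1 scores cycles cancelled for excessive response as zero oocytes, whereas SAP 9.4 puts them in the 15-or-more and 20-or-more groups.
- **Opposition within a category is undocumented.** This stands. A reader might infer that ESTHER-1 showed opposite effects on these categories. Protocol 1.1 gives each category in one stratum only, from an overseas trial with a different comparator.
- **The fitted rates are rough.** This stands. The negative binomial fit gives 37.6% for 15 or more in the high-AMH comparator group, against the reported 35%. With fitted high-AMH rates of 27.5 v 37.6, the condition is met in 10-28% of trials, against 21-28% with a significant unconditional test. Another fit, with SDs of 4.5/6 to 5.5/7.5, gives 40-44% for the unconditional test on fewer than 4, with the condition met in 6-9%.

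**Conclusion.** The condition is a poor screen, and a better method costs almost nothing. Under the assumed opposing rates the loss is about 15-24 points, in a setting where the unconditional test itself succeeds in only 18-26% of trials. This rests on opposing effects within each category, on the assumed stratum shares, and on reading the cross-reference as including the condition. Little is lost if the other stratum shows no effect, and the loss as a share of significant interactions falls if the high-AMH effect is larger.

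Stronger readings are not supported:
- **Most interactions will be missed.** In the first table 85-95% of significant interactions fall where the condition fails, but that is a share of a minority of trials under assumed rates.
- **Stratum effects will be hidden.** They will not be; SAP 9.1 presents them regardless.
- **The non-inferiority claim is affected.** It is not; it rests on the oocyte count alone.
- **The point extends to the other response endpoints.** For 20 or more oocytes (high AMH 10 v 16, low AMH assumed 1.1 v 0.6) a zero cell occurs in 70-89% of simulated trials, which is a different problem. For 8-14 oocytes, the combined extreme-response definitions and the cancellation composite, protocol 3.5.4 gives no reason to expect opposing effects.

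**What to change.** Keep the existing sentence in SAP 9.4, since it is the only interaction provision for the other endpoints that share it, and add:

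*For retrieval of fewer than 4 and of 15 or more oocytes, the treatment-by-AMH-stratum interaction (ratio of odds ratios with 95% CI and p-value) will be reported beside the by-stratum results, whatever the p-values of the main effects. It is exploratory, of low power and without multiplicity control; a non-significant interaction does not show equal effects. If a cell is zero or sparse, stratum-specific risk differences with exact confidence intervals will be given instead.*

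The cost is one sentence, one model term for two endpoints and a sparse-data fallback. No new data, sample size change or protocol amendment is needed; the SAP introduction already allows for additional analyses. The downside is a few more exploratory p-values, with CIs reaching about a factor of 4-7 either way.
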